### 1.2.3 Rational for Selection of Induction Therapy

The rationale for anti-thymocyte globulin (ATG) induction immunosuppression includes prevention of autoimmune recurrence in transplanted islets via deletion of autoreactive memory cells, prophylaxis of islet allorejection, avoidance of the use of calcineurin inhibitors (CNIs) in the immediate post-transplant period, induction of regulatory T cells with reduced requirements for maintenance immunosuppression, and attenuation of non-specific inflammatory responses to transplanted islets, thereby maximizing engraftment and functional survival of transplanted islets and the success rate of single-donor islet transplants. Two polyclonal anti-thymocyte antibody preparations have been marketed in the United States, Thymoglobulin® and ATGAM®. Two randomized double-blind clinical trials indicated that Thymoglobulin® is more efficacious than ATGAM® for induction immunosuppressive therapy and for the treatment of acute graft rejection episodes in adult renal transplant recipients (58, 59). Thymoglobulin® induction therapy achieved rejection-free allograft survival in 96% of the patients. The incidence of cytomegalovirus (CMV) disease in the first year was 12.5%, and no patient developed posttransplant lymphoproliferative disease (PTLD). ATG is known to contain a variety of anti-adhesion molecule antibodies (60). It interferes with leukocyte responses to chemotactic signals and inhibits the expression of integrins required for firm cellular adhesion. Such mechanisms of action may account for the effect of ATG on non-specific inflammation and reperfusion injury and may explain the 1% incidence of delayed graft function in kidney recipients (58, 60-63). Recent studies have shown that early administration of a variety of antibodies directed at adhesion molecules reduces graft dysfunction, and acute and chronic rejection associated with ischemia-reperfusion injury and brain death (64).

The resistance of islet-directed autoimmune responses to conventional immunosuppressive drugs (65-69) and the immediate exposure of intraportally transplanted islets to primed autoreactive, islet beta celldirected T cells provide a strong rationale for pre-transplant initiation of ATG, which is known to cause selective depletion of activated T cells and dose-dependent depletion of resting T cells (70). Experimental data suggest that the protection of whole pancreas transplants from recurrent autoimmunity is functionally related to the inclusion of a significant quantity of lymphoid tissue (possibly containing an immunoregulatory T cell subset) as part of the pancreas graft and not to immunosuppression alone (71, 72). Clinical evidence also indicates that destructive anti-islet autoimmunity persists for decades after manifestation of T1D (66, 73, 74) and that type 1 diabetic individuals with long disease duration do not spontaneously anergize their autoreactive effector Th1 cells and/or restore Th2 or other regulatory T cell function. Accordingly, reprogramming the recipient's immune system seems to be of paramount importance if autoimmune recurrence in transplanted islets is to be prevented.

Maki et al. demonstrated that immunotherapy of non-obese diabetic (NOD) mice with ALS after development of overt autoimmune diabetes leads to long-lasting abrogation of autoimmunity(75). ALS given within 14 days of disease onset gradually reversed hyperglycemia with a 76% cumulative incidence of remission. Diabetic NOD mice that failed to respond to ALS treatment accepted subsequent islet isografts for a prolonged period (mostly >100 days), indicating that autoimmunity was abrogated in the latter animals in which extensive irreversible beta cell destruction had already occurred by the time of ALS treatment. These experimental findings are corroborated by clinical observations reported by the Brussels group (76). Of 7 islet-after kidney recipients treated in Brussels, only the 3 patients who had received ATG as induction immunosuppressive therapy during the first 10 days following their previous kidney transplant showed long-term islet graft survival. Furthermore, according to an analysis performed by the International Islet Transplant Registry on all 50 insulin-independent, type 1 diabetic islet allograft recipients transplanted through 1999, 23 had received single-donor islet transplants, and 19 of those 23 had received anti-thymocyte or anti-lymphocyte globulin for induction immunosuppression and 1 had received ATG at the time of a previous pancreas transplant (77). It is conceivable that the need for 2-3 donor pancreata as a source of islets in the Edmonton experience reflects the inability of the induction immunotherapy to completely abrogate the anti-islet autoimmune response. Even a low level of persistent autoimmunity may interfere with the function of transplanted islets via pro-inflammatory cytokine mediated inhibition of insulin secretion. The ATG immunotherapy as proposed in this trial may be advantageous due to the deletion/inhibition of anti-islet directed autoreactive T cells.

In the event that a second or third transplant is required to achieve or maintain insulin independence, the monoclonal anti-interleukin-2 receptor antibody basiliximab will be used to limit the total dose of ATG administered to any one recipient. Induction immunotherapy with anti-interleukin-2 receptor antibody is a critical component of the steroid-free immunosuppressive protocol recently developed for islet transplantation by the Edmonton group (5).

The immunosuppression regimen for the subsequent islet transplants will be identical to the regimen for the initial islet transplant with the exception of the Thymoglobulin®. Basiliximab will be used instead of Thymoglobulin® for all subsequent islet transplants. The safety and efficacy of basiliximab has previously been documented in multi-center trials in renal transplantation. When added to therapy with cyclosporine, Azathioprine, and prednisone, basiliximab reduced the frequency of acute rejection and did not affect graft or patient survival. At six months, there were no significant differences between the basiliximab and the placebo group with respect to infectious complications or cancers[82]

### 1.2.3 Rational for Selection of Study Population

Iatrogenic hypoglycemia is a major unresolved problem for many patients with T1D. It is the limiting factor in the management of T1D, causing some deaths as well as recurrent physical, and recurrent (or even persistent) psychosocial, morbidity (Cryer, Fisher et al. 1994).

Neuroglycopenia can cause social embarrassment, and even lead to ostracism or be mistaken for disorderly or unlawful behavior(Cryer, Fisher et al. 1994). The more distressing the severe hypoglycemic episode, the greater the psychological fear of hypoglycemia(Irvine, Cox et al. 1992). The threat and fear of severe hypoglycemia can significantly discourage patients and health care providers from pursuing intensive insulin therapy and can therefore be a major but unrecognized impediment to achieving euglycemia(Irvine, Cox et al. 1991; Cryer, Fisher et al. 1994). Pramming et al. found that their patients were as concerned about the development of severe hypoglycemia as they were about the development of blindness or renal failure (Pramming, Thorsteinsson et al. 1991).

Ryan et al. documented the absence of episodes of severe hypoglycemia in 12 successful islet transplant recipients (median follow-up, 10.2 months) (Ryan, Lakey et al. 2001)whose diabetes was complicated by recurrent episodes of severe hypoglycemia pretransplant. This would suggest that hypoglycemia associated autonomic failure associated with defective counterregulation and impaired sympathodrenal responses is not just due to recurrent hypoglycemia. After a sustained period without any hypoglycemia most patients post islet transplant still had defective responses to hypoglycemia. The absence of clinically significant hypoglycemia post islet transplant despite the persistent defect in counterregulation in most subjects demonstrates the dominance of the absence of glucose regulated insulin secretion in the pathogenesis of severe hypoglycemia. Correction of this can only currently be attained with transplantation of beta cell tissue.

The risk of an islet transplant and of the associated immunosuppressive treatments is particularly justifiable in the subgroup of patients whose T1D is complicated by hypoglycemia-associated autonomic failure (as clinically manifested by hypoglycemia unawareness and a history of recurrent severe hypoglycemia). For the subgroup of patients unable to continue intensive insulin therapy because of recurrent severe hypoglycemia, an islet transplant may currently be the only approach to achieving the benefits of euglycemia, without the risks associated with hypoglycemia or with the extensive surgery required for a vascularized pancreas transplant. Thus, the potential direct benefits to this subgroup are sufficient to offset the risks of participation in islet transplant trials.

### **1.3 Investigational Product**

The manufacturer of the drug substance LWM-DS (Mw 5000Da) is pK Chemicals A/S (Köge, Denmark). The final product of Low Molecular Weight Sulfatated Dextran (LMW-DS 20 mg/mL) is manufactured by Apoteket AB, Produktion & Laboratorier (Umeå, Sweden) with an average molecular mass 5000 Da. LMW-DS for the clinical trial will be produced in compliance with EU-GMP.

### **1.4 Concomitant Immunosuppressive Medications**

The protocol includes the following induction drugs; Rabbit anti-thymocyte globulin (ATG, Thymoglobulin®) for the initial islet transplant, for a second or third transplantation a monoclonal IL-2 receptor blocker, Basiliximab (Simulect®), replaces Rabbit anti-thymocyte globulin. In addition, the protocol contains one cell proliferation inhibitor (CellCept® *or* Rapamune®) and one calcineurin inhibitor (Prograf® *or* Sandimmune Neoral®). The protocol includes one Anti-Inflammatory agent, Etanercept (Enbrel®).

If there are no contraindications the patient should receive maintenance immunosuppression of full dose CellCept and low dose Prograf. The immunosuppressive treatment should be adapted to side effects and tolerability. A clinically motivated switch of immunosuppressive medications, among the drugs listed above, is not to be seen as a protocol deviation.

# 1.5 Known and Potential Risks to Human Participants

### 1.5.1 Low Molecular Weight Sulfated Dextran

Prolonged oral administration and infusion of LMW-DS (molecular mass 8 kDa) have been associated with thrombocytopenia after 3-7 days. The thrombocytopenia led to bleeding complications (e.g. epitaxis) in some cases. In none of these studies, however, were serious bleeding events reported. Reversible alopecia was seen in 50% of the patients who received the LMW-DS for more than 8 days. In the present study, LMW-DS will not be used for more than 6 hours and side effects of the kind reported above are therefore not expected. This notion has been confirmed in a recently performed phase I study with a treatment protocol, targeting an APTT of 150±10s was tested. This concentration did not affect platelet count or function and did not increase the risk of bleeding. No other adverse events were reported. Immobilized dextran sulfate has been used to treat patients with hyperlipidemia by plasmapheresis (Thompson 2003). Anaphylactoid reactions with hypotension have been reported in patients treated with ACE-inhibitors due to activation of the contact system, therefore on the morning of the islet transplant, ACE inhibitors should not be administered to the participant. Unlike high molecular weight dextran sulfate, however, soluble LMW-DS does not activate the contact system and is therefore not anticipated to produce this side effect.

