# **Study Definitions Page**

Control Arm- State of the Art	The study treatment group randomized to receive protocol specified immunosuppression without LMW-DS, including anticoagulative treatment with Heparin with the islet infusion.
Experimental Arm- Low Molecular Weight Sulfated Dextran	The study treatment group randomized to receive protocol specified immunosuppression with Low Molecular Weight Sulfated Dextran (LMW-DS), and excluding Heparin treatment.
Full Islet Graft Function	
 
Islet transplant recipients are considered to have full islet graft function if all of the following criteria are met: 
 
Titrated off insulin therapy for at least 1 week (7 consecutive days) with the last day within the day 75 and day 365 windows;
 
One HbA1c level, one fasting serum glucose level, and Mixed Meal Tolerance Test are documented within the visit window (e.g. 70-80 days at Day 75) and 7 consecutive days of blood sugar and insulin readings are documented within +/- 7 days of the visit window (e.g. 63-87 days at Day 75);
 
HbA1c <7.0% or a ≥2.5% decreased from baseline;
 
Fasting capillary glucose level should not exceed 140 mg/dL (7.8 mmol/L) more than three times in the 7 consecutive days (fasting is defined as 1st blood sugar reading of the day not noted as post-prandial or bedtime). Post-prandial capillary glucose level ≤ 126 mg/dL (≤7.0 mmol/L) at 90 minutes during the MMTT;
 
Fasting serum glucose level ≤ 126 mg/dL (≤7.0 mmol/L) from central lab results; if the fasting serum glucose level is > 126 mg/dL (>7.0 mmol/L), it must be confirmed in an additional one out of two measurements;
 
At least one MMTT fasting or stimulated c-peptide ≥0.5 ng/ml.
 
 
 

Graft Failure	Islet allograft failure will be defined as absence of insulin production by transplanted islets, as evidenced by absence of c-peptide <0.1nmol/L (<0.3 ng/mL). This will be determined by: (1) c-peptide <0.1nmol/L (<0.3 ng/mL) on random testing, followed by (2) c-peptide <0.1nmol/L (<0.3 ng/mL) at baseline, and at 60 and 90 minutes after MMTT. C-peptide levels obtained in the course of the MMTT levels will be run at the core laboratory in Seattle, WA. Subjects with graft failure do not need to complete the day 75 metabolic assessment.

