### **2. OBJECTIVES**

# 2.1 Primary Objective

The primary objective is to evaluate the safety and efficacy of Low Molecular Weight Dextran Sulfate (LMW-DS) to enhance engraftment and prevent IBMIR in islet transplantation to Type 1 diabetic subjects.

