### 4.1.4 Safety Endpoints

### At 75 $\pm$ 5 days and 365 $\pm$ 14 days following the first islet infusion:

- The incidence and severity of adverse events related to the islet infusion procedure including: bleeding (> 2 g/dl (20g/L) decrease in hemoglobin concentration); segmental portal vein thrombosis; biliary puncture; wound complication (infection or subsequent hernia); and increased transaminase levels (> 5 times ULN)
- The incidence and severity of adverse events related to the immunosuppression including: allergy; reduction in GFR; increase in urinary albumin excretion; addition or intensification of anti-hypertensive therapy; addition or intensification of anti-hyperlipidemic therapy; oral ulcers; lower extremity edema; gastrointestinal toxicity; neutropenia, anemia, or thrombocytopenia; viral, bacterial, or fungal infections; and benign or malignant neoplasms
- The incidence of immune sensitization defined by detecting anti-HLA antibodies not present prior to transplantation
- The incidence of a change in the immunosuppression drug regimen

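### The adverse-event endpoints are defined by relatedness to the infusion procedure or to immunosuppression, so none is defined for LMW-DS or heparin, and the relatedness they need is not collected for non-serious events

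*Protocol*

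**What the plan says.** Section 2.1 makes the safety of LMW-DS, together with its efficacy, the primary objective.

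Section 4.1.4, repeated in the Synopsis, has two adverse-event endpoints at day 75 and day 365 after the first infusion. The first is "The incidence and severity of adverse events related to the islet infusion procedure including: bleeding (> 2 g/dl (20g/L) decrease in hemoglobin concentration"; its list goes on to portal vein thrombosis, biliary puncture, wound complications and raised transaminases. The second opens "The incidence and severity of adverse events related to the immunosuppression including: allergy; reduction in GFR" and further on names "neutropenia, anemia, or thrombocytopenia; viral, bacterial, or fungal infections". The other safety endpoints are immune sensitization, a change of immunosuppressive regimen and worsening retinopathy.

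On attribution, Section 8.3.1 says that it is determined and collected for serious adverse events alone, by the site investigator, in relation to an investigational product. Section 8.5 identifies the investigational product as LMW-DS.

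On the hazards, Section 1.5.1 reports that prolonged oral dosing and "infusion of LMW-DS (molecular mass 8 kDa) have been associated with thrombocytopenia after 3-7 days". Because exposure here is at most 6 hours, it concludes that "side effects of the kind reported above are therefore not expected". It mentions anaphylactoid reactions in patients on ACE inhibitors, directly after a sentence on immobilized dextran sulfate, and adds that "soluble LMW-DS does not activate the contact system and is therefore not anticipated to produce this side effect".

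**The concern.** The arms differ in one thing: LMW-DS or heparin around the islet infusion. A safety endpoint that serves the primary objective should be able to show a difference caused by that contrast. Here the events most relevant to it, apart from bleeding, are named only as consequences of a treatment that both arms receive. Read literally, a platelet fall or allergic reaction put down to LMW-DS or heparin belongs to neither endpoint.

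The condition also requires a causal judgment that the protocol does not arrange to record. Whoever builds the endpoint table must either infer causes afterwards, in an open-label trial, or ignore the condition. Either way the published count would not be the one that the protocol defines.

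**Working it through.** The protocol gives no figure to reproduce. The check is to set the sections side by side.

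1. **Is LMW-DS or heparin part of the immunosuppression?** No. Section 1.4 lists the immunosuppressive and related drugs and includes neither. The Study Definitions describe the experimental arm as immunosuppression with LMW-DS added. Table 1 in Section 5.1 lists LMW-DS and heparin as separate regimen items. An event caused by either is therefore not immunosuppression-related.

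2. **Does the open-ended list help?** Both lists begin with the word including, so other event types may be added. The requirement of relatedness still governs each item, so the list can grow in event types but not in causes.

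3. **Can the condition be evaluated?**
 - Non-serious events: under Section 8.3.1, no attribution is collected. Section 8.3.2 sets follow-up for events possibly or probably related to the trial product, which suggests that some judgment is made more widely. That judgment still concerns the trial product, not the procedure or the immunosuppression.
 - Serious events: attribution is recorded against the investigational product. An event coded as related to LMW-DS points away from both endpoint categories. An event coded as unrelated does not show which category it belongs to.

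4. **What remains outside the endpoints?** Section 8.3 records all adverse events whatever their relation to treatment. Section 8.3.1 requires reporting from grade 2. Section 10.1 analyses safety by treatment received. Section 10.5 summarises adverse events by body system and overall in the reports to the monitoring board. The events are not lost; they are only missing from, or undefined in, the named endpoints.

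5. **Can the bias be sized?** Let b be the control rate, e the true excess with LMW-DS, q the share of LMW-DS-arm events attributed to LMW-DS, and h the share of control-arm events attributed to heparin. If attributed events are left out, the counted difference is (b + e)(1 − q) − b(1 − h). As pure illustration, take b = 0.30 (the ATG figure in Section 1.5.2.1) and an assumed e = 0.10:
 - q = 0.25, h = 0: 0.40 × 0.75 − 0.30 = 0.
 - q = 0.25, h = 0.25: 0.30 − 0.30 × 0.75 = 0.075.
 - q = 0, h = 0.25: 0.40 − 0.225 = 0.175.

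 The true difference is 0.10, so the counted one may be too small or too large. No document gives e, q or h. Even b does not carry over: it comes from kidney recipients on 1.5 mg/kg/day for 7 to 14 days (10.5 to 21 mg/kg in total), whereas Section 5.5 gives 6 mg/kg.

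6. **What could an all-cause count show with 18 per arm?** With b = 0.30, about 18 × 0.30 = 5.4 controls would be affected. Exact Fisher power for assumed excesses of 10, 20 and 30 points is 5%, 16% and 36%. With no events in 18, the one-sided 95% upper bound is 1 − 0.05^(1/18) = 15.3%. A clean count is descriptive rather than decisive, but it can be interpreted.

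**The case against.** The best defence has four parts.

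- **Safety capture is broad.** All events are recorded, safety is analysed by treatment received, serious events are attributed to LMW-DS, and Section 6.2 suspends enrolment for an unexpected fatal or life-threatening event possibly related to the test therapy. This stands. A reader might infer that LMW-DS toxicity disappears from the trial's safety data; the documents do not support that.

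- **LMW-DS and heparin may count as part of the procedure.** Both are given with the islets (Sections 5.2.2 and 5.3), and bleeding, a central concern with both, is a named procedure event with a hemoglobin threshold. This is a possible reading, and it means that bleeding is largely covered. But the protocol does not adopt it, both drugs are also infused for 5 hours after the islets, and thrombocytopenia and allergy remain listed under the other cause.

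- **The hazards are remote.** A reader might take thrombocytopenia and anaphylactoid reaction as established hazards of this product at this exposure. Section 1.5.1 does not say so: the product here is 5 kDa, exposure is short, and the phase I study showed no effect on platelets. That study was in normal subjects, however (Section 1.2.2), and the protocol still excludes dextran hypersensitivity and withholds ACE inhibitors on the transplant morning. An expectation of safety is what the trial should be able to check.

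- **Final tables belong in the SAP.** That is fair for table layout. The causal restriction is written into the endpoint definition in the protocol itself.

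**Conclusion.** The point holds as a defect of endpoint definition. The two adverse-event endpoints depend on causes that exclude the randomised treatment, and on a relatedness judgment that is not collected for non-serious events. A serious event attributed to LMW-DS fits neither endpoint.

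Its reach is limited to the named endpoint counts; the adverse-event database and the body-system summaries are intact. It would be tempting to conclude that the safety comparison is biased towards LMW-DS by a definite amount. That needs an assumed excess, an assumed share attributed to LMW-DS and no attribution to heparin. None of these is in the documents, and the sign of the error changes with them.

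The conclusion rests on reading the relatedness wording literally and on LMW-DS and heparin not being immunosuppressants. The first is how the text stands; the second is supported by Section 1.4, the Study Definitions and Table 1. The change is worth making because it serves the primary objective and is close to free.

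**What to change.** In Section 4.1.4 and the Synopsis, define three safety endpoints counted regardless of attribution and compared between arms by treatment received:

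- thrombocytopenia, by incidence and severity, using the CIT-TCAE grading already named in Section 8.3.1;
- bleeding, with the existing hemoglobin threshold;
- allergic or anaphylactoid reaction, including hypotension during the infusion.

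Take thrombocytopenia and allergy out of the list that requires relatedness to immunosuppression. A separate alopecia endpoint is not needed: Section 1.5.1 reports it only after more than 8 days of dosing.

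The data are already collected. Appendix 1 schedules platelets at days 1, 3, 7, 14, 21, 28 and 75. Section 5.2.4 sets the hemoglobin measurements around the transplant. Section 5.2.5 and footnote 9 of Appendix 1 cover vital signs, and Section 8.3 the adverse-event records. Because Section 5.2.5 stands under the LMW-DS heading, state that its vital-sign schedule applies in both arms, so that ascertainment is equal.

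The cost is a change of wording in two places and one safety table, with no new visit or sample.
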